3.7. Table of endpoints/outcomes

Objectives	Outcome Measures	Timepoint(s)
Primary Objective Participant clinical status (on a 7- point ordinal scale) In accordance with WHO recommendations the primary endpoint will be determined by a pilot trial of the first 100 participants.	 7-point ordinal scale: Not hospitalised, no limitations on activities Not hospitalised, limitation on activities; Hospitalised, not requiring supplemental oxygen; Hospitalised, requiring supplemental oxygen; Hospitalised, on non-invasive ventilation or high flow oxygen devices; Hospitalised, on invasive mechanical ventilation or ECMO (Extracorporeal membrane oxygenation) Death. 	Up to day 29
Secondary Objectives	Outcome Measures	Timepoint(s)
Evaluate the clinical efficacy of Brensocatib relative to standard care in adult patients hospitalised with COVID-19	Clinical Severity Time to an improvement of one category from admission using 7-point ordinal scale. Participant clinical status on 7-point ordinal scale Mean change in the 7-point ordinal scale	Daily whilst hospitalised Days 3, 5, 8, 11, 15 and 29. Baseline to days 3, 5, 8, 11, 15 and 29.
	National Early Warning Score (NEWS): Time to discharge or to a NEWS of ≤ 2 and maintained for 24 hours, whichever occurs first. Change from baseline Oxygenation:	Daily whilst hospitalised Days 8, 15, 29
	Oxygen free days Incidence and duration of new oxygen use during the trial	1-29 days 0-29 days
	Mechanical Ventilation: Ventilator free days	1-29 days

	Incidence and duration of new mechanical ventilation use during the trial.	1-29 days
	Hospitalisation:	
	Duration of hospitalisation (days).	Date of admission and discharge
	Mortality:	
	28-day mortality	Date of death
Evaluate the safety of the	Cumulative incidence of SAEs	1-29 days
intervention through 28 days of follow-up as compared to the control arm	Discontinuation or temporary suspension of treatment	1-29 days
	Changes in white cell count, haemoglobin, platelets, creatinine, total bilirubin, ALT, and AST over time (hospitalised participants only)	Days 0/1, 3, 5, 8, 11, 15, 29
	Adverse events of special interest- hyperkeratosis, infections and dental complications	1-29 days
	dental complications	
Exploratory Objectives	Outcome Measures	Timepoint(s)
Exploratory Objectives Evaluate the virologic efficacy of Brensocatib	·	Timepoint(s) Day 15 and day 29

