It is expected that these clinical assessments will be carried out by the clinical team during routine clinical care and documented on a NEWS chart. Where the assessments have been carried out, the results of the assessment closest to 8am on the day will be used to prevent duplication and further exposure of the trial staff to patients with COVID-19.

- Blood pressure and pulse, lying or seated
- Tympanic temperature
- SpO2
- Record if SpO2 has been measured on air or oxygen concentration the participant was receiving.

Ordinal Scale

The ordinal scale is an assessment of the clinical status on a given trial day. Each day, the worst score for that day will be recorded. The scale is as follows:

- 1. Not hospitalised, no limitations on activities
- 2. Not hospitalised, limitation on activities;
- 3. Hospitalised, not requiring supplemental oxygen;
- 4. Hospitalised, requiring supplemental oxygen;
- 5. Hospitalised, on non-invasive ventilation or high flow oxygen devices;
- 6. Hospitalised, on invasive mechanical ventilation or ECMO;
- 7. Death.

NEWS Score

The NEWS score has demonstrated an ability to discriminate patients at risk of poor outcomes. (Smith, 2016). This score is based on 7 clinical parameters. The NEWS2 Score is being used as an efficacy measure.

This should be evaluated at the assessment recorded closest to 8am on a given trial day. These parameters can be obtained from the hospital chart.

Exploratory assessment- viral shedding

Where practical at the Tayside site only, nasal swabs will be obtained on day 15 and day 29 to evaluate viral clearance by PCR.

Exploratory assessment- neutrophil studies

At the Tayside and Sheffield sites only, additional blood will be taken for isolation of peripheral blood neutrophils, as per outcome measures section 3.7.

Exploratory assessment- quality of life

The validated EQ-5D-5L quality of life tool will be administered to patients who are able to complete the questionnaire either in person (those still in hospital) or over the telephone (those at home) to determine the impact of treatment on quality of life.

Clinical Evaluation

As these participants are in-patients receiving care for COVID-19, they will be monitored as per clinical need. Where already obtained for clinical need the following blood results will be recorded at days 1, 3, 5, 8, 11, 15, 29:

- White cell count, haemoglobin, platelets, neutrophils, eosinophils, lymphocytes
- creatinine, eGFR
- AST and ALT

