Participants discharged home will not receive further safety assessments. It is not necessary to perform further blood tests on inpatients for the purposes of safety. Routine blood tests taken as part of routine clinical care will be used. If tests are not performed for clinical reasons they will be treated as missing data for analysis.

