8. TRIAL TREATMENTS

8.1. Name and description of investigational medicinal product (IMP)

	Investigational Medicinal Product	Dosage, form and strength
Arm 1	Brensocatib (INS1007)	25mg once daily
Arm 2	Placebo	25mg once daily

Treatment is administered for 28 days in total.

Tablets will be dispensed in bottles containing 35 tablets. Participants will be given the bottle allocated to them on discharge and instructed to take the tablets only for a total of 28 days. Written information, Participant Diary, will be given telling them when to stop taking their tablets. Participants will also be phoned on day 29 as per Schedule of Procedures, at this point they will be reminded that they should stop taking their tablets.

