9. PHARMACOVIGILANCE

9.1. Definitions

Term	Definition
Adverse Event (AE)	Any untoward medical occurrence in a participant to whom a medicinal product has been administered, including occurrences which are not necessarily caused by or related to that product.
Adverse Reaction (AR)	An untoward and unintended response in a participant to an IMP which is related to any dose administered to that participant.
	The phrase "response to an IMP" means that a causal relationship between a trial medication and an AE is at least a reasonable possibility, i.e. the relationship cannot be ruled out.
	All cases judged by either the reporting medically qualified professional or the Sponsor as having a reasonable suspected causal relationship to the trial medication qualify as ARs. It is important to note that this is entirely separate to the known side effects listed in the SmPC. It is specifically a temporal relationship between taking the drug, the half-life, and the time of the event or any valid alternative etiology that would explain the event.
Serious Adverse Event	A SAE is any untoward medical occurrence that:
(SAE)	 results in death is life-threatening requires inpatient hospitalisation or prolongation of existing hospitalisation results in persistent or significant disability/incapacity consists of a congenital anomaly or birth defect Other 'important medical events' may also be considered serious if they jeopardise the participant or require an intervention to prevent one of the above consequences.
	NOTE: The term "life-threatening" in the definition of "serious" refers to an event in which the participant was at risk of death at the time of the event; it does not refer to an event which hypothetically might have caused death if it were more severe.
Serious Adverse Reaction (SAR)	An adverse event that is both serious and, in the opinion of the reporting Investigator, believed with reasonable probability to be due to one of the trial treatments, based on the information provided.
Suspected Unexpected Serious Adverse Reaction (SUSAR)	A SAR, the nature and severity of which is not consistent with the information about the medicinal product in question set out in the reference safety information.

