9.2. Operational definitions for (S)AEs

Deterioration of the existing condition, COVID-19, with the exception of death, or known side-effects recorded as primary or secondary endpoints are not reported as (S)AEs or (S)ARs but are recorded separately. All events resulting in deaths will be reported as SAEs.

The following events will be deemed as expected in participants with COVID-19 and will not be recorded as AEs:

- cough
- pyrexia
- headache
- tiredness
- diarrhoea
- aches and pains
- nasal congestion
- runny nose
- sore throat
- Anosmia
- Loss of taste
- deterioration in renal and or liver function and changes in full blood count parameters; these will be recorded as endpoints for the evaluation of safety of the IMP

Anticipated AEs for the trial drug are be listed in the Reference Safety Information these would not be considered to be SUSARs unless the severity of the event was considered to be unexpected.

All SAEs and SARs will be reported to sponsor, see section 9.3, with the exception of hospitalisation as this is recorded as an end point.

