9.8. Overdose

An overdose will be defined as taking more than 50mg of trial medication in a 24-hour period.

Whilst in hospital, the trial medication will be held and given to participants as per drug record by the clinical team. On discharge from hospital, participants will take home enough medication to complete 28 days of treatment.

An overdose itself is not an AE. However, if the overdose results in clinical signs and symptoms, it requires expedited reporting as if it is an SAE. In the case of an overdose, the PI or delegate should use clinical judgment in treating the overdose, and inform the Sponsor immediately.

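### Protocol 9.2 keeps renal, liver and blood-count changes off the AE log with no limit of setting, but the endpoint meant to hold them covers inpatients only, so a non-serious event found after discharge has no direct place of record

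*Protocol*

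**What the plan says.** Protocol 9.2 lists twelve kinds of event that are regarded as expected in COVID-19 and are not to be recorded as AEs. Eleven are symptoms. The twelfth is "deterioration in renal and or liver function and changes in full blood count parameters; these will be recorded as endpoints", and it is the only item given a replacement place of record. No time, setting or severity limit is attached.

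The replacement is the laboratory safety endpoint in Protocol 3.7, which ends "ALT, and AST over time (hospitalised participants only". Section 7.8 says "Where already obtained for clinical need the following blood results will be recorded at days 1, 3, 5, 8, 11, 15, 29", and then "Participants discharged home will not receive further safety assessments".

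Treatment does not stop at discharge. Protocol 8.1 says "Participants will be given the bottle allocated to them on discharge", and 9.8 says "participants will take home enough medication to complete 28 days of treatment". The AE window in 9.3 runs from consent to day 29.

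On serious events, 9.2 sends all SAEs and SARs to the sponsor "with the exception of hospitalisation as this is recorded as an end point", while 9.1 keeps as a seriousness criterion an event that "requires inpatient hospitalisation or prolongation of existing hospitalisation".

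**The concern.** The exemption and its replacement have different scopes. In hospital, a rise in creatinine or a fall in neutrophils is left off the AE log but appears in the laboratory data. At home, it is left off the AE log and there are no laboratory data.

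This matters because such events can still come to light. Under 9.3, staff check medical records for AEs and hospitalisations at every data collection point and call. A kidney injury managed by a GP could be found in this way and then, under 9.2, not be logged. It would also miss the causality and severity assessment that 9.3 applies to AEs.

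The period affected is relevant to the drug. Protocol section 2 says that the effect builds over several days, with the largest reductions in elastase seen at day 28 in the phase 2 study. Appendix 1 names neutropenia among the key risks to monitor. Section 2.1 has the DMC review AEs, SAEs and laboratory data, and a non-serious post-discharge event of this kind is in none of the three.

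**Working it through.** **Tracing the rules**

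1. AE log: closed to these events by 9.2, with no limit, for the whole window to day 29.
2. Laboratory endpoint: inpatients only (3.7). In Appendix 4, full blood count, urea and electrolytes, and liver function tests from day 3 onwards carry the footnote that they are not done once the participant is discharged. The unscheduled-assessment column has none of them. The schedule in SAP 5.4 is the same.
3. SAP 10.5 mentions day 15 and day 29 results for participants who can return to clinic. That conflicts with both schedules, covers only two days, and SAP 14 declares no change to the protocol.
4. SAE route: open if the event is serious. Deaths are reported under 9.6.
5. Indirect traces: Appendix 4 records concomitant medication at days 8, 15 and 29 with no in-hospital restriction. Discontinuation or suspension of treatment is a safety endpoint, and 7.11 requires withdrawn participants to be described with their reasons, if known. A readmitted participant counts as hospitalised again, but bloods are recorded only if the stay covers a recording day.

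A non-serious event found after discharge therefore has no direct record under steps 1 to 4, only the traces in step 5.

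**Scale, from the plan's own assumptions**

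Inputs: the placebo distribution in Protocol Table 4 (from worst to best 2, 1, 2, 7, 8, 38 and 42%), 200 per arm (400 at 1:1), and the odds ratio of 1.75 in Protocol 10.1.

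- Check against Table 6 (odds ratio 2): placebo out of hospital 38 + 42 = 80%, odds 4. Active odds 4 x 2 = 8, so 8/9 = 88.9%. Table 6 gives 29.7 + 59.2 = 88.9%, which agrees.
- Odds ratio 1.75: active odds 4 x 1.75 = 7, so 7/8 = 87.5%. Out of hospital: 160 + 175 = 335 of 400 (83.75%). With no treatment effect it is 160 + 160 = 320.
- Alive in hospital, placebo: 1 + 2 + 7 + 8 = 18%, or 36 of 200.
- Alive in hospital, active: death odds (0.02/0.98)/1.75 = 0.01166, so 1.15% die. Then 100 - 87.5 - 1.15 = 11.35%, or about 23 of 200.
- If AE logging of these events began only at discharge, the active arm would have 175/160 = 1.09 times as many eligible participants by day 29 (177.8/160 = 1.11 at odds ratio 2) with no drug harm at all.

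These figures are a snapshot at day 29, the day after dosing ends. Table 6 labels the same scenario day 15. They show how few participants could supply late laboratory data. They do not measure days on drug at home.

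**The case against.** The strongest reply is that 9.2 has a second reason for the exemption: these events are deemed expected in COVID-19. The other eleven items have no replacement endpoint either, so losing the endpoint at discharge does not remove the whole basis. That is right, and limiting laboratory data to inpatients is a disclosed choice. But 9.2 also says that these changes will be recorded as endpoints, and after discharge they are not.

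The remaining gap is also narrow, because serious events, SARs, deaths and treatment interruption are all captured somewhere. This stands and sets the limits of the point.

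The documents do not support four stronger readings that a reader might infer.

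- That neutropenia stopping the drug is counted only as a discontinuation. Non-serious neutropenia does fall outside the SAP 10 display of AEs leading to discontinuation, but 7.11 requires the reasons for withdrawal to be described.
- That the between-arm AE comparison turns on whether a site follows 9.2 or the SAP. SAP Table 13 does list acute kidney injury, abnormal liver function tests and raised transaminases. But sites record under the protocol and eCRF, the SAP tables are reporting templates, and such terms could arise as SAEs. Allocation is blinded and stratified by site, so differences in site practice should be broadly balanced.
- That readmissions are lost. The exception in 9.2 is ambiguous, but the endpoint it refers to is duration of hospitalisation, 9.1 keeps the seriousness criterion, and SAP Table 11 has a row for events requiring hospitalisation. Together these favour reporting. One clarifying sentence is enough.
- That a number of lost events can be derived from the 335. The documents give no event rate and no discharge timing.

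A last objection concerns the remedy. Bloods are taken for clinical need in hospital, and inpatient numbers are expected to differ by arm (36 against about 23). Adding these events to the main AE comparison would make detection depend on setting. That stands, and the fix allows for it.

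**Conclusion.** The gap is real and follows from the protocol's text: an exemption without a setting limit, a replacement endpoint for inpatients only, dosing at home to day 28, and continued record checks. The rule discards non-serious renal, liver and haematological events that staff have already found, leaving only indirect traces.

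The size in events is unknown. The plan's scenario puts about 84% of participants out of hospital by day 29 at an odds ratio of 1.75, so the late laboratory tables would describe a small group selected by outcome. No bias between arms from the present rule has been shown, and the primary efficacy result is unaffected.

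The conclusion assumes that the closing sentence of 9.2 governs serious events. The section's opening sentence also sets aside COVID-19 deterioration (other than death) and known side effects recorded as endpoints, so a serious event placed in one of those classes might not be reported. The point is worth correcting because the correction is short and needs no new data collection visit.

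**What to change.** 1. In Protocol 9.2, limit the exemption to laboratory changes captured as in-hospital endpoint values. Log clinically significant renal, liver or haematological events (diagnosed, treated, leading to drug interruption, or neutrophils below 1.0 x 10^9/L) as AEs throughout days 1-29, in or out of hospital. Do not start at discharge, for the reason shown by the 1.09 ratio. Tabulate these events by arm in a separate display, outside the main Poisson comparison. SAP 10.2 takes in every reported AE, so this carve-out must be written into SAP 10 and 10.2.
2. In Protocol 9.2, state that the hospitalisation exception covers only the index COVID-19 admission, so that a readmission caused by an untoward event is reported as an SAE.
3. In SAP 10.5 and Table 10, label the laboratory results as in-hospital data and give the number tested per arm and day. Make the return-to-clinic wording agree with the schedule, either by deleting it or by providing for it there.

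The cost is a few sentences in 9.2, SAP wording and one extra table, with no new visits or blood tests. The downsides are some extra AE and SAE entries, each needing review within 24 hours under Appendix 5, some double recording of in-hospital events, and a judgement of clinical significance. Testing stays more frequent in hospital, so the separate display should say so.

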9.3. Recording and reporting of SAEs, SARs AND SUSARs

AEs will be recorded on the AE Log in the eCRF and will be assessed for severity and causality by the CI or PI. AEs occurring from the time a participant consents to join the trial until the participant's day 29 will be recorded. An AE may be classified as a SAE or AR. An initial assessment of expectedness/listedness for SAEs will be conducted by the PI based on the Reference Safety Information (RSI).

Participants discharged from hospital before the end of trial will be given a diary to record adverse events, this will be used as an aide memoire for them to report AEs at the telephone follow-up call. This diary will not be returned to the trial staff.

The PI will make a clinical judgment as to whether or not an AE is of sufficient severity to require the participant's discontinuation of treatment. A participant may also voluntarily discontinue treatment due to what he or she perceives as an intolerable AE. If either of these occurs, the participant should be given appropriate care under medical supervision until symptoms cease, or the condition becomes stable.

AEs and SAEs will be followed up until recovered/recovered with sequelae/death or for 30 days after participant's day 29 whichever happens first. SUSARS will be followed until resolution.

The CI, PI or delegate will check the medical records for the occurrence of AEs and hospitalisations at every data collection point/telephone call during the trial. Serious AEs (SAEs) will be submitted on an SAE form to the Sponsor Pharmacovigilance Section [contact] within 24 hours

of becoming aware of the SAE. All SAEs need to be assessed and signed off by the PI or a delegated doctor within the 24hr reporting window. Site PIs will also notify the CI when submitting an SAE.

The evaluation of expectedness will be made based on the knowledge of the reaction and the relevant safety information (RSI) in the Brensocatib Investigators Brochure (IB) (see section 9.4). The Sponsor will make the definitive assessment on expectedness for the purposes of SUSAR reporting.

The Sponsor is responsible for reporting SUSARs to the UK competent authority, the MHRA, and the Research Ethics Committee (REC). Fatal or life threatening SUSARs will be reported within 7 days and non-fatal and non-life threatening SUSARs within 15 days.

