## Safety of the intervention:

- 1. Cumulative incidence of serious adverse events (SAEs) from day 1 to 29.
- 2. Discontinuation or temporary suspension of treatment from days 1 to 28.

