#### 9.2.11 Duration of hospital stay - days

Duration of hospitalization will be calculated only for participants who are discharged alive on or prior to Day 29 and will be compared between the treatment arms using negative binomial regression.

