## Oxygenation

No of days free from oxygen

Duration of new oxygen use

Mechanical ventilation

Number of patients receiving new mechanical ventilation

No of days free from ventilation

Duration of new ventilation used

Duration of hospital stay - days

28-day mortality

Table 10: Safety analyses

	Brensocatib N =	Placebo N =	Effect estimate (95% CI)
% of patients with at least 1 AE			
Incidence of SAEs			
Discontinuation or temporary suspension of treatment			
Changes in white cell count			
Changes in haemoglobin			
Changes in platelets			
Changes in creatinine			
Changes in total bilirubin			
Changes in ALT			
Changes in AST			
Adverse events, n (%):			
Hyperkeratosis (Skin)			
Infections			
Dental complications			

Table 11: Adverse Events

Adverse Event - n (%)	Brensocatib	Placebo
	N =	N =
Death		
Life-threatening		
Required hospitalisation		
Resulted in persistent or significant disability		
Medically significant		
Total		

Table 12: Summary of all adverse events - System Organ Class Level

N = N =	Total	Placebo	Brensocatib
	N=	N =	N =

Number of participants

Number of participants with adverse events

Number of participants without adverse events

Number of adverse events

Cardiac disorders

Eye disorders

Gastrointestinal disorders

General disorders and administration site conditions

Infections and infestations

Injury, poisoning and procedural complications

Investigations

Metabolism and nutrition disorders

Musculoskeletal and connective

tissue disorders

Nervous system disorders

No Code

Psychiatric disorders

Renal and urinary disorders

Respiratory, thoracic and mediastinal disorders

Skin and subcutaneous tissue

disorders

Vascular disorders

Table 13: Summary of all adverse events - Preferred Term Level

Brensocatib	Placebo	Total
N =	N =	N=

Number of participants

Number of participants with adverse

events

Number of participants without adverse

events

Number of adverse events

Abdominal discomfort

Abdominal pain

Acute kidney injury

Arthralgia

Back pain

Blood glucose increased

Bradycardia

Cerebrovascular accident

Chest discomfort

Chest pain

Clostridium difficile infection

Constipation

Cough

Delirium

Diarrhoea

Dizziness

Drug eruption

Dry mouth

Dry skin

Dysarthria

Dyspepsia

Dyspnoea

Dysuria

Electrocardiogram abnormal

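### Protocol 9.2 exempts hospitalisation from SAE/SAR reporting to the sponsor without limit, citing an endpoint that does not record readmission

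*Protocol*

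**What the plan says.** Protocol 9.1 treats an event as serious if, among other criteria, it "requires inpatient hospitalisation or prolongation of existing hospitalisation". Protocol 9.2 then says "All SAEs and SARs will be reported to sponsor, see section 9.3", but adds "with the exception of hospitalisation as this is recorded as an end point". An earlier sentence of 9.2 separately exempts deterioration of COVID-19 other than death, and 9.2 has every event resulting in death reported as an SAE.

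Protocol 9.3 has SAEs sent to the sponsor within 24 hours of awareness. Appendix 5 repeats this. Neither mentions a hospitalisation exception. On recording, as distinct from reporting, 9.3 says "AEs will be recorded on the AE Log in the eCRF", with assessment of severity and causality, and has medical records checked for adverse events and hospitalisations at each contact.

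The endpoint given as the reason appears in the Protocol 3.7 table as duration in days, with the timepoint "Date of admission and discharge". SAP 9.2.11 narrows it: "Duration of hospitalization will be calculated only for participants who are discharged alive on or prior to Day 29".

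On the analysis side, SAP 4.2 lists "Cumulative incidence of serious adverse events (SAEs) from day 1 to 29" as a safety outcome. SAP Table 11 has a row "Required hospitalisation", and Table 14 includes hospitalisation among the actions taken for an adverse event.

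**The concern.** Exempting an event from SAE reporting because it is an endpoint is reasonable only if the endpoint captures the same event with the detail that safety review needs. Here it does not. A length of stay cannot show that a participant went home, continued the tablets and was readmitted with, say, an infection, which is one of the adverse events of special interest in Protocol 3.7.

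Two things are at stake. The first is sponsor oversight: under 9.3 the sponsor makes the definitive expectedness judgement for SUSAR purposes, and the exception covers SARs as well as SAEs. The second is the SAE incidence in the SAP, if it depends on what reached the sponsor.

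Other safety data are thin in the same period. Treatment runs to day 28, at home for those discharged. Protocol 7.8 provides no further safety assessments after discharge, so adverse events are found through telephone calls and record checks.

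**Working it through.** The documents give no expected SAE or readmission rate, so there is no plan figure to reproduce. The check sets the passages side by side.

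1. **Scope of the exception.** Section 9.2 names hospitalisation and sets no limit by admission, timing or cause. Prolongation of a stay is a separate limb of the 9.1 criterion and is not named in 9.2.
2. **Match between exception and endpoint.** The endpoint (Protocol 3.7, SAP 9.2.11) yields a number of days for those discharged alive by day 29. It has no field for a second admission, its cause or its relatedness.
3. **Other capture of readmission.** The 7-point scale scores a readmitted participant 3 to 6 on an assessment day. After discharge, the scheduled days in Appendix 4 are 3, 5, 8, 11, 15 and 29, which leaves 29 − 15 = 14 days between the last two. The scale carries no cause. It is a partial backstop.
4. **Would a narrow reading rescue the sentence?** Suppose it means only the enrolling admission. Section 6.1 requires participants to be in-patients before randomisation, and 9.3 collects adverse events from consent, so in the ordinary course that admission is not a trial adverse event. COVID-19 deterioration is already exempt. The narrow reading leaves the sentence little to do. What remains is mainly hospitalisation for other reasons.
5. **Recording.** Section 9.3 keeps the underlying adverse event on the eCRF log and allows it to be classified as an SAE. SAP Tables 11 and 14 expect hospitalisation in the adverse event data.
6. **Source of the SAE count.** Neither SAP 4.2 nor SAP section 10 says whether SAE incidence comes from the AE log or from sponsor SAE forms. Under-counting depends on this.

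**Illustration of the worst case only.** Assume, with no support in the documents, that SAE incidence is built from sponsor forms and that a share f of participants with SAEs in each arm is lost because hospitalisation was the only seriousness criterion. With n = 400/2 = 200 per arm and two-sided 0.05, the recorded risks are p(1 − f), and

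power = Φ{[Δ − 1.96√(2p̄(1 − p̄)/n)] / √([p₁(1 − p₁) + p₂(1 − p₂)]/n)}.

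For 10% v 20% and f = 0: [0.10 − 1.96 × √(2 × 0.15 × 0.85/200)] / √((0.09 + 0.16)/200) ≈ 0.85, giving power 0.802.

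| f | Recorded, true 10% v 20% | Power | Recorded, true 20% v 30% | Power |
|---|---|---|---|---|
| 0 | 10 v 20 | 0.802 | 20 v 30 | 0.638 |
| 10% | 9 v 18 | 0.752 | 18 v 27 | 0.578 |
| 25% | 7.5 v 15 | 0.661 | 15 v 22.5 | 0.485 |
| 50% | 5 v 10 | 0.475 | 10 v 15 | 0.327 |

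An equal proportional loss leaves the risk ratio unchanged but shrinks the risk difference and the power to see it. If f is zero, because the count uses the AE log, nothing is lost.

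**The case against.** The strongest reply is that the sentence governs what is sent to the sponsor, not what is recorded or analysed. The adverse event behind an admission still goes on the log with a causality assessment, records are checked for hospitalisations, and SAP 10.2 includes all reported adverse events. Infections are reported separately as events of special interest. Protocol 2.1 has the DMC review adverse events as well as SAEs. Events that are fatal, life-threatening, disabling or medically important meet other criteria, and 9.10 sends any SUSAR to the sponsor. The hospitalisation row in Table 11 suggests the authors expected these events in the data.

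Most of this stands, and it rules out a stronger reading. A reader might infer that readmissions are captured nowhere, or that they necessarily fall out of the SAE incidence. The documents do not support either inference. Nor do they support extending the exception to prolonged stays, which 9.2 does not name. That the endpoint covers only the enrolling stay is itself an inference from the admission and discharge dates; the documents do not say so.

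The reply does not repair sponsor reporting. Recording an event at site is not notifying the sponsor. Section 9.10 helps only once an event has been recognised as a SUSAR, and the definitive expectedness judgement in that process belongs to the sponsor, who may not have received the report.

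**Conclusion.** The point holds as a conflict between 9.2 and the combination of 9.1, 9.3, Appendix 5 and SAP Table 11, with a stated reason that does not fit. SAEs and SARs that are serious only because of hospitalisation after discharge may go unreported to the sponsor and so bypass expectedness and SUSAR review. Under-counting in the day 1 to 29 SAE incidence is a possibility that depends on the unstated data source.

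The size cannot be estimated from the documents. It is tempting to take the planned control-arm share not in hospital at day 29 (42% + 38% = 80%, Protocol 10.1 Table 4), apply it to 400 to get 320, and assume 5–10% readmitted, giving 16–32 exempt events. That should not be used as the size. The readmission rate has no source in the documents, the 80% is a status at one day in one arm, some readmissions would meet another seriousness criterion, and COVID-19 deterioration is exempt under a different sentence. The power table likewise rests wholly on assumed risks and losses. The case for change rests on the text: the exception as written points the wrong way for safety reporting and is cheap to correct.

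**What to change.** In Protocol 9.2, limit the exception to the admission for COVID-19 during which the participant was enrolled, with wording that also covers existing in-patients who enter under the 6.1 footnote. State that an adverse event leading to a new admission after discharge, other than the separately exempted COVID-19 deterioration, is reported as an SAE under 9.3. Check that 9.1, 9.2, 9.3 and Appendix 5 then agree.

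In the SAP, state that SAE incidence and Table 11 use all AE-log events classified as serious, reconciled with the sponsor SAE forms before database lock. The reconciliation would also find any readmission already logged but not sent to the sponsor.

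The cost is a protocol wording change, a modest number of extra SAE forms and one reconciliation check.
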